Inclusion Criteria: Subjects with CF (medical record evidence of cystic fibrosis transmembrane conductance regulator mutation or sweat chloride test or nasal voltage difference, **and** 1 or more clinical findings of CF), age 12 or greater with an FEV₁ >30% predicted (within the last 14 days) and oxygen saturation \geq 90% on FiO₂ \leq 50%, admitted for an exacerbation, able to provide written informed consent or assent.

Exclusion Criteria: Pregnancy, hemoptysis more than 60 mL within the last 30 days, use of any investigational study drug within the last 30 days, initiation of hypertonic saline within the last 30 days, known intolerance to hypertonic saline, serum creatinine 2 mg/dl or more, active malignancy in the last year, on waiting list for lung transplantation, received a solid organ transplant, lack of FEV₁ data from the last 14 days and previous participation in this study.

Experimental Treatment: Aerosolized 15% xylitol, 5 ml twice a day for 2 weeks using Pari LC nebulizer with Vios compressor, (Pari Inc, Monterey, CA) . Xylitol crystals are

made as food additives by Danisco Cultor, USA. Aerosol solution is sterile, non-pyrogenic, preservative-free solution for inhalation made by UI Pharmaceuticals (Iowa City, IA).

Control Treatment: Hypertonic 7% saline (UIHC pharmacy) 4 ml twice a day for 2 weeks using the same kind of nebulizer.

Screening and Baseline Visit: On the day of admission for exacerbation, informed consent obtained in subjects whose admission spirometry (or spirometry within the last 14 days prior to admit date) shows an FEV₁ >30% predicted. Once consented, subjects will be randomized to either xylitol or saline group as per the randomization code previously generated by the statistician. Demographics, current medications use and the revised CF quality of life questionnaire (CFQ-R) will be completed. Spontaneously expectorated sputum will be collected and processed for cell count and cytokines and quantitative cultures. Blood will be collected for chemistry and liver function tests (LFT). Pregnancy test will be done in women. All medication use during hospitalization will be recorded. Treatment will begin the day after admission for an exacerbation. Results from spirometry that is routinely done twice a week for inpatients will be recorded. All spirometry testing will follow the 2005 American Thoracic Society guidelines.

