First dose pre and post spirometry: All subjects will undergo spirometry before and 20 minutes after the first study drug dose as follows.

Perform baseline spirometry and measure SpO₂. Multiply the patient's best FEV₁ by 0.80 to obtain 20% fall in FEV₁ value.

Premedicate subject with 4 puffs albuterol and wait 15-30 min.

Begin study drug nebulization.

Wait for 15-30 minutes and repeat spirometry and SpO₂.

Subject is excluded from the study if SpO₂ is <89% or FEV₁ declines by 20% or greater from baseline.

Administration: Subjects will take their routine inhaled medicines followed by chest physical therapy. All subjects will then receive 2-4 puffs of albuterol metered dose inhaler 15-30 minutes before the study drug. Finally the study drug will be inhaled. All empty, unused and partially used study drug containers will be tracked by the investigators. Subjects will be required not to use any new treatments if not medically indicated during the study period.

Day 14 follow-up: Subjects will undergo spirometry and sputum collection and answer CFQ-R questionnaire. Blood draw for LFTS and electrolytes will be done if not done for clinical reasons. If subjects are discharged prior to 14 days of xylitol use, nebulizer solutions will be sent home. They will be asked to keep a log of nebulizer use and bring back empty and unused vials on follow-up visit (Day 10-15, preferably day 14). They will undergo spirometry and sputum collection and questionnaire administration on that day. If subjects don't return on this day, they will have a phone follow-up for adverse events and compliance.

Phone follow-up: Week 1, Day 90 and Day 180 after discharge: Subjects will be contacted by phone at these time points to enquire about further pulmonary exacerbations, admissions, and other AEs.

In the event of bronchospasm: Subjects will alert the nurses or study team members. Nebulized bronchodilators will be immediately administered. Once symptoms resolve, they will undergo spirometry using a portable handheld spirometer by a trained user. If the subjects dropped FEV₁ by 20% or greater from their baseline, they will not receive further study drug. However, they will remain in the study for completion of data collection.

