Endpoints: Primary outcome will be FEV₁ change from baseline. Other safety assessments include vital signs within 30 minutes after nebulization, withdrawal from the study, rescue bronchodilator use, incidence of treatment related adverse events, and laboratory tests (chemistry and liver function tests). Efficacy outcomes include difference in density of colonization per gram of sputum from baseline to day 14, time to next hospitalization, difference in CFQ-R, sputum cytokine levels and cell counts.

Adverse events such as cough, chest tightness, and headache will be scored on a visual analog scale. Other variables collected include antibiotic and other medication use during the hospitalization, demographics, organ involvement with CF, genotype data from medical records. Follow-up phone calls will be made 1 week, 3 months and 6 months

after study completion for any complications and to assess the time to next hospitalization.

Adverse events: Any untoward medical occurrence (abnormal symptom, sign or laboratory value) in a study subject that is temporally associated with the study drug will be reported as an adverse event. The event does not have to have a causal relationship with the treatment. The event will be classified by the investigator as mild, moderate or severe. The relationship of an adverse event to the study drug will be determined by the investigator to be ‘unlikely to be related, possibly related, probably related or definitely related’.

Future Use of Stored Specimens

Subjects will be asked for permission to keep any remaining unlinked sputum and blood specimens for possible use in future research studies. Samples may be shared with other investigators at other institutions. The samples will not be sold or used directly for production of any commercial product. No human genetic tests will be performed on samples. Each sample will be labeled only with a study ID to protect subject’s confidentiality.

There are no benefits to subjects in the future research use of their specimens. Reports about future research done with these samples will not be kept in their health records.

Subjects can decide if they want their samples to be used for future research or have their samples destroyed at the end of the study. A subject’s decision can be changed at any time prior to the end of the study by notifying the study investigators in writing.

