However, if a subject consents to future use and some of their specimens have already been used for research purposes, the information from that research may still be used.

Statistical analysis: We plan to enroll a total of 60 subjects for this study. These subjects will be randomly assigned to the treatment (xylitol) and control (saline) groups, with a goal of 30 subjects in each group. Since this is a pilot safety study, it has been primarily powered to detect common adverse events. Assuming that the likelihood of a subject experiencing an adverse event is no less than 5%, a sample size of 30 subjects ensures 80% power towards event detection [16]. (In other words, with a group sample size of 30, the probability of observing at least one adverse event in the group is at least 80%.)

Study Performance

Accrual will be assessed on a monthly basis. We will examine the number of screened subjects, those meeting eligibility criteria, the number of persons consenting to participate and the number of randomized. The rate of accrual will be tracked versus the expected number to achieve the target of 60 participants randomized.

We will also track the completion number and proportion by time. The number of study terminations and reason for termination will be measured. The subject will undergo a spirometry and if the FEV₁ has declined by 20%, the subject will be terminated from the study.

Baseline

The composition of the study sample will be described in aggregate. Comparison of randomized participants of baseline characteristics will be analyzed using 2 sample t-test,

Wilcoxon rank sum test, and analysis of variance (ANOVA) as indicated by the type and characteristics of the variable.

Outcomes

To assess the adequacy of these group sample sizes for testing a trend in efficacy, we consider the outcome of log CFU. We assume an average density of colonization of 6.5 log CFU with a SD of 1.5 log CFU among CF subjects. To detect a reduction of 1.5 log CFU in the xylitol group with 80% power, the required sample size is 17 subjects per group. (This computation is based on a two-sided, two-sample t-test conducted at the 0.05 level of significance.) Data from all patients who have received at least one dose of the drug or placebo will be analyzed. Thus, the analysis will be based on intention to treat. All tests will be two-sided, and conducted using a significance level of 0.05.

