The primary outcome is FEV₁ change from baseline. To test for a difference in the mean change between the treatment group and the control group, a two-sample t-test will be conducted. To estimate the difference in the mean change, the equivalent confidence interval procedure will be used. Prior to conducting the test, normality will be assessed for each group based on normal probability plots. If gross departures from normality are observed, a Wilcoxon rank sum test will be performed instead of the t-test. (With group sample sizes of 30, the t-test is fairly robust to departures from normality.)

The same analytical approach will be used to assess differences in the group means for the following variables: the primary outcome of change in respiratory symptom score, and the efficacy outcomes of change in density of colonization (per gram of sputum),

change in sputum cytokines and cell counts, and responses to all Likert-scale questions on the CFQ-R.

To analyze group differences in the efficacy outcome of time to next exacerbation, a time-to-event analysis will be conducted. Kaplan-Meier estimates will be obtained for each survival curve (where failure is defined by exacerbation). To compare the survival distributions, a log rank test will be employed.

To compare the proportion of subjects in each group who have experienced any adverse events, Fisher's exact test will be used. Since certain subjects may experience multiple adverse events, we will also compare the incidence of adverse events in each group. For this comparison, a test will be conducted to contrast the mean number of events in each group, where the two samples of event counts are treated as arising from independent Poisson distributions. To estimate the difference in group proportions and the difference in group means, equivalent confidence interval procedures will be employed.

The preceding inferential procedures will be conducted for individual types of adverse events (e.g., cough, chest tightness, headache), as well as the aggregate of all adverse events. Fisher's exact test will also be used to compare the compliance proportion and the proportion of rescue bronchodilator use in each group.

Since this study is a randomized, controlled clinical trial, we expect the treatment group and the control group to be balanced with respect to factors that could affect the primary

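### Every CFQ-R question is tested separately at an unadjusted 0.05, with no single CFQ-R result defined and the use of baseline left unclear

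*Combined protocol and SAP*

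**What the plan says.** The Endpoints section lists among the efficacy outcomes "difference in CFQ-R, sputum cytokine levels and cell counts". The Abstract places CFQ-R among the outcomes for a trend in efficacy.

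The Outcomes part of the Statistical analysis section first describes the FEV₁ analysis: a two-sample t-test on mean change, the matching confidence interval, and a Wilcoxon test if normality fails grossly. It continues: "The same analytical approach will be used to assess differences in the group means for the following variables". The list that follows covers change in respiratory symptom score, change in density of colonization, "change in sputum cytokines and cell counts", and finally "responses to all Likert-scale questions on the CFQ-R". The general rule is "All tests will be two-sided, and conducted using a significance level of 0.05".

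CFQ-R is collected twice. Under Screening and Baseline Visit, "the revised CF quality of life questionnaire (CFQ-R) will be completed"; under Day 14 follow-up, "Subjects will undergo spirometry and sputum collection and answer CFQ-R questionnaire".

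No section names a CFQ-R domain, summary score or key question, a multiplicity rule, or a power statement for CFQ-R. Analysis of covariance is offered at the end of the Statistical analysis section, but only as a replacement for the t-test if a marked imbalance between groups is observed.

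**The concern.** An endpoint worded as one quantity is analysed as a set of separate tests, one per question, each at 0.05. Nothing says which of them answers the question of whether quality of life differed between groups. With no effect at all, some questions can be expected to cross 0.05, and the plan gives no rule for reading them. The answers come from patients in a trial whose protocol says blinding is not assured because xylitol tastes sweet, so a free choice among items adds to an outcome already open to bias.

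There is also a gap on baseline. The other outcomes in the sentence are expressed as change and CFQ-R is not, although both measurements exist. Two analysts could follow the text and produce different results, one on Day 14 answers and one on change.

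**Working it through.** **Plan's own figure.** None exists for CFQ-R. The only efficacy sample size is for log CFU: difference 1.5, SD 1.5 (1.0 SD), 80% power, two-sided 0.05. The noncentral t calculation gives 16.7, rounded up to 17 per group, as stated.

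**Inputs from the documents.** 30 per group ("with a goal of 30 subjects in each group"); two-sided 0.05 per test; no multiplicity rule; CFQ-R at baseline and Day 14.

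**Assumed inputs, not in the documents.** Number of questions k from 10 to 50; common inter-item correlation r of 0, 0.5 or 0.7; an effect of 0.5 SD; baseline-to-Day 14 correlation ρ of 0.3 to 0.7.

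**Step 1: expected false positives under no effect.** This is 0.05 × k, whatever the correlation: 0.5 at k = 10, 2.5 at k = 50.

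**Step 2: chance of at least one.** For independent questions it is 1 − 0.95^k. For correlated questions, take test statistics Z = √r·C + √(1−r)·E, with C a shared and E a separate standard normal, and find the probability that any |Z| exceeds 1.96.

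| k | Independent | r = 0.5 | r = 0.7 |
|---|---|---|---|
| 10 | 0.40 | 0.29 | 0.21 |
| 20 | 0.64 | 0.42 | 0.29 |
| 30 | 0.79 | 0.51 | 0.34 |
| 50 | 0.92 | 0.62 | 0.40 |

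One prespecified score tested once gives 0.05. Correlation lowers the chance of any false positive but makes false positives cluster. Dividing Step 1 by Step 2 at r = 0.5, the mean number given at least one is 0.5/0.287 = 1.7 at k = 10 and 2.5/0.622 = 4.0 at k = 50.

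**Step 3: baseline adjustment, 30 per group, 0.5 SD effect.** A Day 14 comparison ignoring baseline has 48% power. ANCOVA multiplies the variance by 1 − ρ², so the standardised effect becomes 0.5/√(1−ρ²). An unadjusted change score has standardised effect 0.5/√(2(1−ρ)).

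| ρ | Day 14 only | Change score | ANCOVA |
|---|---|---|---|
| 0.3 | 48% | 36% | 51% |
| 0.5 | 48% | 48% | 59% |
| 0.7 | 48% | 69% | 76% |

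**Step 4: a multi-item score.** The SD of a mean of m items is √((1+(m−1)r)/m) in item SD units. For an illustrative six items at r = 0.4 this is √(3.0/6) = 0.707.
- All six shift by 0.5 SD: effect 0.5/0.707 = 0.707 SD, power 77%.
- All six shift, r = 0.7: SD √(4.5/6) = 0.866, effect 0.577 SD, power 59%.
- Four of six shift, r = 0.4: effect (4/6 × 0.5)/0.707 = 0.471 SD, power 43%.
- Two of six shift, r = 0.4: effect (2/6 × 0.5)/0.707 = 0.236 SD, power 15%.

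The comparator is 48% for one affected item tested alone at unadjusted 0.05.

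**The case against.** **The outcome is exploratory.** This is a pilot safety study. CFQ-R is one of several trend outcomes, and no stopping rule or success criterion depends on it. That stands and limits the weight of the point. It does not remove it, because the plan prescribes formal tests at 0.05 and does not label the CFQ-R results descriptive.

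**Baseline may already be used.** A reader might infer that the plan analyses raw Day 14 answers and discards the baseline. The documents do not establish this. In the Endpoints section the CFQ-R difference follows directly after a colonization difference defined from baseline to Day 14, and the approach carried over to CFQ-R was set up for mean change. Change may be intended. What stands is that the sections do not settle it. If change is meant, the item-by-item testing remains, and an unadjusted change score gains over Day 14 alone only when ρ exceeds 0.5.

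**The sizes rest on assumptions.** They do. The 92% figure needs 50 independent questions, which is implausible within one questionnaire; the correlated columns are the better guide.

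**Low power is not shown.** A reader might also infer that the CFQ-R analysis is underpowered and that a summary score is bound to help. The documents set no CFQ-R target effect. At the 1.0 SD assumed for log CFU, a single question has 97% power with 30 per group. A score helps if the effect is shared across items and loses if it is confined to a few, as Step 4 shows.

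**Intervals are arguably planned.** The confidence interval is part of the approach extended to CFQ-R. That is fair, but intervals for every question still do not define one result.

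**Conclusion.** The point holds in a limited form. On the plain text, every CFQ-R question is tested separately at 0.05, nothing identifies the result that answers the endpoint, and the sections leave open whether baseline is used. The false-positive risk is several times the 5% of a single test over the whole assumed range of 10 to 50 questions at correlations up to 0.7. The direction does not depend on those assumptions, short of perfectly correlated items; the size does. The gain from baseline adjustment, 48% to about 59%, applies to an assumed 0.5 SD effect and an assumed ρ of 0.5, measured against an analysis that ignores baseline. The consequence is confined to interpretation of the exploratory quality-of-life outcome. It is worth correcting because the change is cheap, but it does not threaten the trial's main conclusion.

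**What to change.** Before results are seen, amend the Endpoints and Outcomes text so that they agree, as follows:

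- Name one CFQ-R score, taken from the questionnaire's own scoring rather than constructed for this trial.
- Compare that score between arms at Day 14 by ANCOVA with the baseline score as covariate, whether or not an imbalance is observed, and report the difference with its confidence interval.
- Report other scales and single questions descriptively with confidence intervals and no significance claims.

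The cost is SAP wording and a scoring step; no new data, visits or subjects are needed. The price is that item-level p-values are given up, and an effect confined to a few questions would be diluted in the score. The descriptive item results keep such a pattern visible.

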University of Iowa

SAFETY OF 2-WEEK USE OF AEROSOLIZED
XYLITOL IN SUBJECTS WITH CYSTIC
FIBROSIS

NCT Number 00928135

[name]
3-16-2012

SAFETY OF 2-WEEK USE OF AEROSOLIZED XYLITOL IN SUBJECTS WITH CYSTIC
FIBROSIS

ABSTRACT

Cystic fibrosis (CF) lung disease is characterized by chronic bacterial colonization and recurrent infection of the airways. Disruption of the cystic fibrosis transmembrane conductance regulator chloride channels in subjects with CF results in altered fluid and electrolyte transport across the airway epithelium thereby initiating infections. Lowering the ASL salt concentration and increasing the ASL volume might therefore potentiate innate immunity and therefore decrease or prevent airway infections in subjects with CF. Xylitol is a 5-carbon sugar that can lower the airway surface salt concentration, thus enhancing innate immunity. We recently tested the safety and tolerability of inhaling increasing concentrations of single doses of hypertonic xylitol (10% followed by 15%) in stable subjects with CF. All six subjects tolerated both the doses well. There was no significant change in FEV₁ or respiratory symptom score. In this protocol, we propose to test the safety and tolerability of aerosolized xylitol used daily for 2 weeks in subjects with cystic fibrosis. In a pilot, 2-week study, 60 subjects with cystic fibrosis with an FEV₁ >30% predicted will be randomized to receive aerosolized 7% hypertonic saline (4 ml) or 15% xylitol, (5 ml) twice a day for 14 days. The primary outcomes will be safety as assessed by FEV₁ change from baseline, adverse events and respiratory symptom score. Outcomes for trend in efficacy include density of colonization per gram of sputum, time to next exacerbation, sputum cytokines and revised CF quality of life questionnaire.

BACKGROUND

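### Every adverse event is graded for severity, but neither planned adverse-event comparison uses the grade, so a shift to more severe events at unchanged incidence and counts would not show in either of them.

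*Combined protocol and SAP*

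**What the plan says.** Under Adverse events, the definition is broad: abnormal symptoms, signs and laboratory values all count, with no causal link required. Each event then gets a grade: "The event will be classified by the investigator as mild, moderate or severe".

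Under Statistical analysis, Outcomes, two between-group comparisons of adverse events are named. The first is per subject: "To compare the proportion of subjects in each group who have experienced any adverse events, Fisher's exact test will be used". The second contrasts mean event counts, "where the two samples of event counts are treated as arising from independent Poisson distributions". Their scope is then widened: "The preceding inferential procedures will be conducted for individual types of adverse events", as well as all events together. No test, table or summary in the statistical section uses the severity grade.

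The Abstract gives adverse events a leading place: "The primary outcomes will be safety as assessed by FEV₁ change from baseline, adverse events and respiratory symptom score". The Endpoints section is narrower. It names FEV₁ change as the primary outcome and lists treatment-related adverse events among the other safety assessments.

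**The concern.** Any/none and event counts give a mild cough and a severe event the same weight. Subjects are inpatients with an exacerbation, the event definition is wide, and the Risks section expects some cough with either treatment. A high any-event proportion in both arms is therefore plausible, although the documents give no rate. Where most subjects have at least one event, any/none has little left to distinguish the arms, and severity is what might still do so.

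The risk is that this safety trial reports no adverse-event difference while moderate and severe events are more frequent on xylitol, with the grades collected and never compared.

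**Working it through.** **Inputs from the documents.** Group size: "with a goal of 30 subjects in each group". Error rate: "All tests will be two-sided, and conducted using a significance level of 0.05". The tests are the two described above. The documents give no event rates by grade, so every severity distribution below is an assumption.

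**The plan's own figure.** The sample-size statement assumes an event probability of 5% per subject and claims at least 80% probability of seeing one or more events in a group of 30. The formula gives 1 − 0.95³⁰ = 78.5%, so the figure reproduces to within two points. It concerns seeing an event in one group and says nothing about comparing arms or grades.

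**Check 1: worst grade per subject.** Four assumed distributions of none/mild/moderate/severe (%), saline vs xylitol:

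- A: 10/60/25/5 vs 10/35/40/15 (pure severity shift)
- B: 20/55/20/5 vs 15/40/30/15
- C: 40/45/12/3 vs 30/40/20/10
- D: 60/30/8/2 vs 45/30/17/8

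In B, C and D the any-event rate also rises: 80 to 85%, 60 to 70% and 40 to 55%.

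*Fisher, any/none.* Power is the sum, over all pairs of counts (i, j), of Bin(i; 30, p_S) × Bin(j; 30, p_X) for those tables with two-sided p ≤ 0.05.

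*Poisson counts.* The plan does not say which two-sample Poisson test it means; the usual normal form is used here. Means are matched to the share with no event, λ = −ln P(none). Then δ = √30 × (λ_X − λ_S) / √(λ_X + λ_S), and power ≈ Φ(δ − 1.96) + Φ(−δ − 1.96).

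- A: λ = 2.303 in both arms, δ = 0, power 5%
- B: 1.609 vs 1.897, δ = 0.84, power 13% (14% by simulation)
- C: 0.916 vs 1.204, δ = 1.08, power 19%
- D: 0.511 vs 0.799, δ = 1.38, power 28%

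*Wilcoxon on worst grade, 0 to 3.* Simulated with ties handled asymptotically; its rejection rate under the null was 4.7%.

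| Scenario | Fisher any/none | Poisson counts | Wilcoxon worst grade | Gain over Poisson (points) |
|---|---|---|---|---|
| A | 0.9% | 5% | 41% | about 36 |
| B | 3.7% | 14% | 33% | about 18 to 20 |
| C | 7.8% | 19% | 25% | about 6 |
| D | 15% | 28% | 31% | about 3 |

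Repeated runs moved the Wilcoxon figures by a point or two, hence the rounded gains.

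**Check 2: equal event rates, only the grade mix changed.** Mean events per subject are the same in both arms. Saline events are 70/25/5% mild/moderate/severe. Xylitol events are 40/40/20% (moderate shift) or 20/50/30% (large shift). There were 3,000 simulated trials per cell.

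| Mean events, shift | Fisher any/none | Poisson | Fisher, moderate or severe | Wilcoxon worst grade |
|---|---|---|---|---|
| 0.7, moderate | 2.7% | 4.8% | 19% | 10% |
| 1.5, moderate | 2.2% | 5.1% | 34% | 36% |
| 2.5, moderate | 0.5% | 4.6% | 42% | 69% |
| 0.7, large | 2.4% | 4.2% | 42% | 18% |
| 1.5, large | 2.5% | 5.3% | 65% | 65% |
| 2.5, large | 0.6% | 5.5% | 76% | 94% |

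Both planned tests stay at their false-positive rates throughout. When events are sparse (0.7 per subject), ties at no event weaken the Wilcoxon test and the moderate-or-severe proportion does better, which is a reason to report both.

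**Precision of the proposed interval.** In scenario A the moderate-or-severe proportions are 30% (25 + 5) and 55% (40 + 15). The half-width is 1.96 × √[(0.30 × 0.70 + 0.55 × 0.45)/30] = 1.96 × √(0.4575/30) = 0.242. The interval is thus about 25 ± 24 points.

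**The case against.** A reader might infer that worse severity would escape all the planned tests. The documents do not support that. Outcomes also tests FEV₁ change, change in respiratory symptom score and the proportion using rescue bronchodilator, and the Risks section names cough and bronchospasm as the expected harms. Worse respiratory events could show there; with 30 per group, the t-test on symptom score has about 80% power for a difference of 0.74 SD. What remains is events outside those measures, such as headache and laboratory abnormalities. Headache is scored on a visual analog scale and laboratory tests are listed as safety assessments, but no analysis of either is named.

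A reader might also measure the gain against Fisher alone, which overstates it. The Poisson test is in the plan too, and recovers much of the difference once incidence rises with severity: in D the gain over it is only about 3 points.

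Nor does it follow that severe events would go unnoticed. Terminations and their reasons are tracked, there is an FEV₁-based stopping rule, and serious unexpected events are reported promptly. A data and safety monitoring plan is cited but not supplied; it may summarise severity, which cannot be checked here. None of these provisions, as far as the documents show, is a between-arm comparison of grade.

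Finally, this is a pilot safety study sized to observe common events, and the protocol concedes that the taste of xylitol may reveal the arm. Resting the aggregate comparison on an investigator's judgement alone would be a poor exchange. That stands, and argues for adding a graded comparison rather than substituting one.

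**Conclusion.** The gap is real but limited. Severity is recorded for every event and used in neither adverse-event comparison, so neither can detect a shift in grade when incidence and counts are unchanged. That much follows from the definition of the tests and needs no assumed rates.

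The size of the loss does rest on assumptions: the severity distributions above, 30 analysed per arm, Poisson event counts and two-sided 0.05. Under the pure shift in A, power is about 1% (Fisher) and 5% (Poisson), against about 40% for Wilcoxon on worst grade. With a simultaneous rise in incidence the advantage over the Poisson test is between about 3 and 20 points. The graded test is itself modestly powered except for large shifts with frequent events, so a non-significant result would not establish equal severity. This is a worthwhile addition to the analysis, and it does not make the planned tests invalid.

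**What to change.** In Statistical analysis, Outcomes, keep the Fisher and Poisson comparisons as they stand and add one graded comparison:

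- Assign each subject the worst severity grade over the study (0 none, 1 mild, 2 moderate, 3 severe) and compare arms by Wilcoxon rank sum test.
- Report the between-arm difference in the proportion of subjects with a moderate or severe event, with its 95% confidence interval.
- State that these are read beside the any-event and count results and do not replace them, because the grader may know the arm.

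The cost is a few sentences; the grades are already collected and no further subjects are needed. The downside is one more comparison, of modest power, on a judged measure. Naming the summary and the moderate-or-severe cut-point in advance avoids choosing them after the data are seen.
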